Assessment calls will occur at Baseline and at 3, 6, 12, and 18 months after Baseline. The primary outcomes are abstinence from tobacco at the 18-month follow-up and abstinence across all follow-ups. Secondary outcomes are smoking quit attempts, cigarettes per day, use of the quitline, and cost-effectiveness. Participants will be scheduled to complete a baseline assessment call within one week. Following the baseline assessment, participants will be randomly assigned to ST or MAPS. Participants will schedule their first counseling call at that time (see Table 1).

Recruitment. Participants will be women with a diagnosis of cervical cancer or high grade cervical dysplasia who report smoking any cigarettes within the past 30 days, recruited through the Stephenson Cancer Center or OU Physicians at the University of Oklahoma Health Sciences Center, via the ClinicalTrials.gov website, by responding to recruitment flyers and internet advertisements (e.g., flyers in clinics, Facebook), and through referrals from healthcare providers.

Participant Eligibility. Inclusion criteria: ≥ 18 ; current smoker with a history of at least 100 lifetime cigarettes and a self-report of smoking within the last 30 days; history of cervical cancer or high grade cervical dysplasia (we have defined survivorship as beginning at the time of cancer diagnosis, consistent with the NCI definition); has a working cell phone; valid home address; speaks English, Spanish or both languages. Exclusion criteria: current use of tobacco cessation medications; self-report of being pregnant or lactating; or, another household member enrolled in the study; or contraindication of nicotine patch use unless under the supervision of a physician as advised by project staff.

Table 1. Schedule of Study Procedures and Assessments	Screening	Baseline	Month 3	Month 6	Month 12	Month 18
Inclusion/Exclusion Criteria	X	X				
Compensation		\$60	\$60	\$60	\$60	\$60
TREATMENT PROCEDURES						
Standard Treatment (ST)	Delivered at Baseline, and Months 6 and 12					
Motivation And Problem Solving (MAPS)	ST plus up to 6 MAPS Counseling Calls delivered over 12 months					
DEMOGRAPHICS, MENTAL HEALTH						
Demographics and Smoking History		X				
Cancer stage at diagnosis, time since diagnosis, current stage, treatment status	X					
Subjective Social Status		X	X	X	X	X
Fear of Cancer Recurrence Inventory (FCRI)	X	X	X	X	X	X
MOTIVATION						
Contemplation Ladder		X	X	X	X	X

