Financial Compensation and Retention Procedures. Participants will receive financial remuneration after completing each assessment call to compensate for the time and inconvenience associated with participation (\$60 for each of the 5 assessment calls and up to a total of \$300). The inclusion of compensation makes study participation more feasible and acceptable, which increases the representativeness of the sample and generalizability of the results. Compensation also increases follow-up rates, which reduces biases, and we have consistently achieved follow-up rates of approximately 80% even among very low-SES and racially/ethnically diverse smokers.^{69,102} Other procedures to reduce attrition include: 1) mailing postcard reminders and calling to remind participants of upcoming assessment calls; 2) maintaining communication with participants throughout the study period via mailing birthday cards, holiday cards, etc. (each mailing includes a stamped address update postcard with the study return address); 3) Having a staff member available at all times during business hours as well as evenings and weekends to conduct assessment calls; 4) requiring that in addition to a functional phone number (necessary for counseling calls), participants must have a home address so that they can be contacted by mail if necessary; and 5) obtaining names, addresses, and phone numbers of up to three collaterals (i.e., relatives/friends) who can provide information on participants' whereabouts during the study (permission to contact the collaterals will be obtained from participants). In addition to being compensated for the time associated with completing assessments, all participants will be compensated up to a total of \$150 for completing the assessments, up to a total of \$150 for costs incurred as a result for the use of study-related cell phone minutes, and up to a total of \$120 for returning the cotinine tests. Compensation for completing assessments will be provided at baseline, 3, 6, 12, and 18 months from baseline (5 times points x \$30 = \$150). Compensation for study-related cell phone use will be provided at baseline, 3, 6, 12, and 18 months from baseline (5 time points x \$30 = \$150). Compensation for returning the cotinine tests will be provided at 3, 6, 12, and 18 months (4 time points x \$30 = \$120).

TREATMENT PLAN

Nicotine Replacement. All participants are eligible to receive a 12-week supply of nicotine patches and

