adjusted for in the *a* and *b*-path analyses. Mediators in the final mediator model will be selected using a backward selection approach.¹¹² We will also compute and compare proportions of mediated effects along with their standard errors across the single and multiple mediator models, as well as across time points where the mediators are measured.¹¹³ A larger proportion of the mediated effect in general suggests a larger mediation effect. Additional mediation analysis for repeated measures abstinence analyses will be conducted using a similar approach with both *a* and *b* paths involving repeated measures analysis, as applicable.¹¹³

Missing Data and Dropouts. It is anticipated that some individuals will drop out or be lost to follow-up, as is typical in smoking cessation treatment studies. Our primary analysis for examining abstinence at 18 months will utilize an intent-to-treat approach by coding missing abstinence data as smoking. However, we will also conduct sensitivity analyses by examining alternative approaches for handling missing data, including multiple imputation (under a missing at random assumption),^{114,115} and selection models (under an assumption of non-ignorable missingness, or missing not at random).^{114,116-118} In the multiple imputation approach, we will conduct analyses to examine whether participants who drop out of the study differ from those who do not, and include those covariates in our multiple imputation models, to mitigate the potential impact of non-ignorable missingness. Regardless of the approach used to handle missing data, it is unlikely that serious biases in estimation or considerable loss of efficiency in inference will result when the proportion of missing data low (e.g., not more than 10%; even more so when the missing data proportions are similar in MAPS and ST).

Overall, robust results based on both the primary and sensitivity analyses will strengthen our study findings.

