Power. Our power analysis is based primarily on the comparison of 18-month abstinence rates between MAPS and ST. Because an intent-to-treat approach will be used, power is calculated based on the full sample without attrition (N=300; 150 per group), given that individuals lost to follow-up will be treated as smoking). All power analyses assume a significance level of 0.05 and a two-sided test. Based on the *Guideline*,²⁰ we estimated that abstinence for ST would be approximately 10%. Using a chi-square test to examine the effect of treatment on abstinence at 18 months, a sample size of 300 (150 per group) will provide 80% power to detect an overall treatment effect that corresponds to abstinence rates of 10% and 21.9% in ST and MAPS respectively. Relative to examining abstinence over time, these calculations represent the worst case scenario. Table 2 presents detectable differences across a range of possible abstinence rates. Analyses conducted using GLMM will have greater power to detect the same average differences across time.

Table 2. Detectable differences in binary smoking outcomes with 80% power (abstinence, quit attempt)	
ST (n=150)	MAPS (n=150)
5.0%	14.60%
10.0%	21.90%
20.0%	34.40%
30.0%	45.70%
40.0%	56.20%

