Although the proposed mediation analyses for aim 2 are theoretically-grounded and hypothesis-driven (see Figure 1), they are quasi-exploratory in nature, and the sample size for this study was based on power to detect a significant difference for Aim 1. Nonetheless, power for the mediation analyses (Aim 2) has been calculated as follows. For the mechanism analyses (Aim 2), power is based on a conservative 25% attrition rate (N= 300; 112 per group). Because the mechanism variables are continuous, a sample size of 300 (112 per group at 18 months) will provide 80% power to detect an effect size of 0.376 standard deviation (SD) unit (difference in means between the ST and MAPS divided by common SD), using a two group t-test with a 0.05 two-sided significance level. Because we have excellent power to detect treatment effects on the primary outcome and mechanisms, as well as the effects of mechanisms on abstinence (with power generally greater using continuous predictors than binary predictors such as treatment group), we expect to have good power to detect mediation effects. We note, however, that the power calculated for analyses in Aim 2 should be considered in the context of inflated type 1 error due to multiple analyses and hypothesis tests (including the mediation analyses) being performed for this aim. We feel that this inflated type 1 error is acceptable given the quasi-exploratory nature of this aim. Nevertheless, future studies focusing on testing specified mediational models should be sufficiently powered using approaches of Fritz and MacKinnon¹¹⁹ or Thoemmes et al.¹²⁰, as appropriate.

Cost Effectiveness

Methods overview. Cost-effectiveness analyses (CEA) will compare the two interventions: ST and MAPS. The conventional CEA summarizes study findings in terms of the incremental cost-effectiveness ratio (ICER).^{121,122} The ICER, calculated as the difference in mean costs between the new and standard treatment divided by the difference in mean effectiveness between the new and standard treatment, estimates the additional resource consumption needed to achieve an increase in an additional unit of effectiveness. The ICER is then compared with a commonly cited or published threshold value associated with an intervention already found to be cost-effective to determine whether a new intervention is cost-effective.

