this study ([name]) to address the issue of missing data using analytical approaches such as multiple imputation or selection models (details see above) and obtain imputed values for individual with missing value in cost and/or effectiveness variable. Next, we will perform deterministic CEA based on ICER. We will then apply the Bayesian approach to construct the CE acceptability curve and conduct probabilistic sensitivity analysis (PSA).^{138,139} The PSA assigns distributions for each of the key parameters to characterize uncertainties in each parameter, propagates all parameter uncertainties through the model simultaneously using simulation methods, and generates an empirical distribution for either the ICER or the net benefit.^{140,141} it has been incorporated in more recent CEA *Guidelines*.¹⁴² We will conduct the Bayesian analysis using WinBUGS, with costs modeled as a gamma or lognormal distribution and abstinence from tobacco or as a binomial distribution.

Finally, we will apply the regression-based cost-effectiveness analysis. Individual-level net benefit will be regressed on covariates, plus a binary variable indicating the ST vs. MAPS arm. Using the "ST" arm as the reference group, the regression coefficients associated with the treatment binary variable will provide information on the cost-effectiveness of the MAPS intervention compared to ST. The regression model will be analyzed in two ways: 1) GLMM to examine how cost-effectiveness varies over time, and 2) Bayesian regression to systematically update information gathered at each time point.

Table 3. Project Phases and Timeline	
Phase 1: 1 Year	Refinement of Treatment Manuals, Counselor Training, Data Management and Tracking Systems, Focus Groups, Pilot Testing
Phase 2: 3.5 Years	Enroll 300 participants, Implement Procedures (Recruitment, Screening, Randomization, Treatment Delivery, Assessment, etc.)
Phase 3: 0.5 Years	Complete Data Analysis and Prepare Manuscripts for Publication

REFERENCES

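### The multiple-imputation variables are chosen by whether dropouts differ from completers, and nothing requires the month 3, 6 and 12 abstinence reports that should best predict month-18 abstinence

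*Combined protocol and SAP*

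**What the plan says.** Under Statistical Considerations, Missing Data and Dropouts, the primary month-18 analysis counts a woman with no abstinence report as smoking. Two sensitivity analyses sit beside it: multiple imputation under missing at random, and selection models under missing not at random. The only rule for choosing imputation variables is that the team will "examine whether participants who drop out of the study differ from those who do not, and include those covariates in our multiple imputation models". The section gives no candidate list, test or threshold. It does not mention treatment arm or earlier abstinence in this context.

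The earlier reports will exist: "Assessment calls will occur at Baseline and at 3, 6, 12, and 18 months after Baseline". Expected loss is not small. Under Financial Compensation and Retention Procedures, "we have consistently achieved follow-up rates of approximately 80" (per cent), and for Aim 2 "power is based on a conservative 25% attrition rate". The plan's reassurance about bias is tied to missingness of no more than about 10%.

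The Analysis part of Cost Effectiveness will use approaches such as multiple imputation or selection models to "obtain imputed values for individual with missing value in cost and/or effectiveness variable". Measures of Effectiveness, just before it, takes the number of quitters from the month-18 primary endpoint.

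**The concern.** Missing at random has to hold given the variables actually in the imputation model. A variable that predicts both dropout and the outcome must be in the model to avoid bias. A variable that predicts only the outcome is worth including for precision. The plan's rule addresses only the dropout side, and only through a difference seen in one sample of perhaps 60 to 75 dropouts (20% to 25% of 300).

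The plan itself treats abstinence as correlated within a woman over time, so her reports at months 3, 6 and 12 should be the best available guide to month 18. If they are left out, a woman last known to be smoking is imputed as though that report did not exist. The sensitivity analysis meant to test the primary result could then agree or disagree with it for the wrong reason.

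**Working it through.** **The plan's own figure.** "All power analyses assume a significance level of 0.05 and a two-sided test"; "a sample size of 300 (150 per group) will provide 80% power" for "abstinence rates of 10% and 21.9% in ST and MAPS respectively". With p̄ = 0.1595,

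n = [1.96√(2 × 0.1595 × 0.8405) + 0.8416√(0.10 × 0.90 + 0.219 × 0.781)]² / 0.119² = 147.4, so 148 per arm.

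Power at 150 per arm is 80.7%, so the figure reproduces. The planned difference is 21.9 − 10.0 = 11.9 points. The documents give no figure for imputation bias.

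**Assumed inputs (not in the documents).** 10% and 21.9% are the true rates. 75% of month-12 abstainers and 6% of month-12 smokers are abstinent at month 18. Loss is d1 among month-12 abstainers and d0 among month-12 smokers, the same in both arms.

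**Month-12 abstinence implied.** a = (p − 0.06)/(0.75 − 0.06)
- ST: 0.04/0.69 = 5.8%
- MAPS: 0.159/0.69 = 23.0%

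**Imputing by arm without month-12 status.** Dropouts receive the completers' rate, so each arm's estimate is

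[0.75a(1 − d1) + 0.06(1 − a)(1 − d0)] / [a(1 − d1) + (1 − a)(1 − d0)]

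| d1 / d0 | ST | MAPS | Difference | Excess over 11.9 |
|---|---|---|---|---|
| 15% / 27% | 10.6% | 23.8% | 13.2 | 1.3 |
| 10% / 28% | 10.9% | 24.8% | 13.9 | 2.0 |
| 20% / 25% | 10.3% | 22.7% | 12.5 | 0.6 (0.55 unrounded) |

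For example, MAPS at 10%/28% is 0.1888/0.7615 = 24.8%.

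**The sign is not fixed.**
- *Arm left out of the imputation model.* At 10%/28% the pooled completers' rate is (0.0798 + 0.1888)/(0.7304 + 0.7615) = 18.0%. ST becomes 7.98 + 0.2696 × 18.0 = 12.8%, MAPS becomes 18.88 + 0.2385 × 18.0 = 23.2%, and the difference is about 10.3, or 1.6 points too small. Over a wider grid with total loss of about 18% to 29%, the bias runs from −1.0 to −2.1.
- *Loss pattern differs by arm (arm in the model; 70% persistence, 4% late quitting).* With ST loss of 10%/30% and MAPS loss of 15%/15%, the completers' rates are 11.5% and 21.9%. The difference is 10.4, a bias of −1.5. With ST 10%/20% and MAPS 10%/32%, they are 10.7% and 25.8%. The difference is 15.1, a bias of +3.2.
- *Equal true rates and equal loss patterns:* bias zero.

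**If the rule is run as a p<0.05 comparison (assumed).** When every dropout has a month-12 report, month-12 abstinence in dropouts versus completers is 8.6% vs 16.4% in the first table row and 5.7% vs 17.4% in the second. The screen flags month-12 status in about 38%, 77% and 10% of trials across the three rows. The average excess is then about 0.3 to 0.6 point. This is below the excess multiplied by the miss rate (1.3 × 0.62 = 0.8 in the first row), because the screen tends to miss in trials where dropouts and completers happen to look alike and the bias is small.

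**Always including month-12 status.** Simulated bias is about zero, and the standard error is about 6% to 10% lower than when it is omitted.

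**Early leavers (70% persistence, 4% late quitting).** If 70% of dropouts leave before month 12, the screen picks up month-12 status in only 17% to 54% of simulated trials. Including month 12 alone still leaves +0.9 to +1.4 points. This is a reason to use months 3 and 6 as well, though it does not prove that they remove the rest.

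**The case against.** The plan does not say that only those covariates will be used, does not restrict them to baseline variables, and names no significance test. A competent analyst might include arm and earlier abstinence anyway. Where the bias is largest, at 10%/28% loss, even a crude p<0.05 screen would usually catch month-12 status if dropouts had reported at month 12. The excess is also modest beside the sampling error: the standard error of the difference is √(0.10 × 0.90/150 + 0.219 × 0.781/150) = 4.2 points, so 0.5 to 2.0 points is roughly 0.1 to 0.5 of a standard error. Nor is imputation the only check. The plan also has selection models, completers-only analyses and a mixed model over all follow-ups.

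All of this stands, and it limits the size of the point. It does not remove it: the one stated rule is keyed to dropout, nothing in the text brings in earlier abstinence because it predicts the outcome, and the screen is unreliable when women leave early.

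A reader might also infer that the cost-effectiveness results inherit this bias. The documents do not establish that. The Analysis part allows imputation or selection models, while Measures of Effectiveness draws quitters from the primary endpoint, where missing is already smoking. The two need reconciling first.

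**Conclusion.** The point holds as a weakness in how one sensitivity analysis is specified. The rule may or may not bring in the month 3, 6 and 12 reports. If it does not, the result is less precise and can be biased either way. With arm in the model and the same loss pattern in both arms, the assumed values give an overstatement of 0.5 to 2.0 points on 11.9. An assumed p<0.05 screen reduces this to about 0.3 to 0.6 on average when dropouts have a month-12 report. Every driver of these figures (persistence, late quitting, loss by smoking status, timing of loss) is an assumption.

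A reader might infer that the plan excludes earlier abstinence, or that its sensitivity analysis will inflate the MAPS effect by 1 to 2 points. Neither is supported: the text is silent on the first, and the direction in the second reverses under equally plausible assumptions. The primary analysis does not use the imputation model and is unaffected. The change is still worth making, because the better model uses data already being collected.

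**What to change.** In Missing Data and Dropouts, state that the imputation model always contains treatment arm (as a term, or by imputing within arm if numbers allow), abstinence at months 3, 6 and 12, and the covariates of the primary logistic model, whether or not dropouts differ on them. Variables found to predict dropout are added to this set.

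Under Cost Effectiveness, state whether the analysis uses the primary-endpoint quitters or imputed abstinence. If imputed, use this same model.

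The cost is about one paragraph of text and no new data. The downside is possible sparse-data instability: 10% of 112 ST completers is about 11 abstinent women, against three earlier reports and eight covariates. A simplified fallback named in advance, such as the last available abstinence report in place of all three, would limit this.

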Reasons for Quitting (Intrinsic and Extrinsic Motivation)		X	X	X	X	X
Motivation		X	X	X	X	X
AGENCY: SENSE OF CONTROL, SELF-EFFICACY, COPING BEHAVIOR						
Sense of Control		X	X	X	X	X
Self-Efficacy Scale		X	X	X	X	X
Coping Inventory		X	X	X	X	X
STRESS, NEGATIVE AFFECT						
Perceived Stress Scale (PSS)		X	X	X	X	X
Positive and Negative Affect Scale (PANAS)		X	X	X	X	X
Depression (CES-D)		X	X	X	X	X
SMOKING-RELATED MEASURES						
Heaviness of Smoking Index (HSI)		X	X	X	X	X
Wisconsin Smoking Withdrawal Scale (WSWS)		X	X	X	X	X
Wisconsin Inventory of Smoking Dependence Motives (WISDM-37)		X	X	X	X	X
SMOKING STATUS, BIOCHEMICAL VERIFICATION, QUITLINE USE						
Smoking Status (SRNT)	X	X	X	X	X	X
Use of the Quitline Cessation Services (including Pharmacotherapy)		X	X	X	X	X
Cotinine (only among participants reporting abstinence)			X	X	X	X
PATIENT REPORTED OUTCOMES						

Functional Assessment of Cancer Therapy – Cervix Cancer (FACT-Cx)	x	x	x	x	x	x
EQ-5D (for health utilities)		x	x	x	x	x

Screening and Informed Consent Procedures. After being screened in-clinic or completing a secure online screener via REDCap, potential participants will be contacted by research staff at Moffitt Cancer Center or Stephenson Cancer Center. All eligible individuals will be invited to participate. A detailed description of the study will be provided and informed consent will be obtained. For those who agree to enroll in the study, research staff will obtain informed consent either in-person or over the phone. When participants are consented over the phone, research staff will read the informed consent document to participants and will document in our database that verbal informed consent has been obtained. A copy of the informed consent document and project materials will be provided to participants either in-person or by mail. All informed consent materials will be available in both English and Spanish. Women who decline or are ineligible will be given self-help materials and a referral to other cessation programs if they so desire.

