Measures of Effectiveness. Two commonly used effectiveness measures in studies comparing the cost-effectiveness of cessation interventions are number of quitters and years of life saved (YOLS).¹³⁶ To facilitate comparing ICER estimated from our CEA with that from other published studies, we will include both measures. The number of quitters in each treatment arm will be retrieved from the primary abstinence endpoint at month 18. We will extrapolate from abstinence to YOLS using a published algorithm that models YOLS per quitter for persons in various age-specific subgroups.¹³⁷ In addition, to assist decision making in selecting among interventions targeted at different conditions that compete for limited budgets, we also included quality-adjusted life year (QALY) as an additional effectiveness measure, and calculate QALY from the health utilities obtained from the EQ-5D. This algorithm was favored over other published methods of extrapolation because it was built from a model with good face validity and has been adopted in many related CE studies.¹³⁶

Analysis. We will compare the cost-effectiveness of the interventions in three time frames: short-term, mid-term and long-term. The short-term and mid-term CEA will use "number of quitters" as the effectiveness measure and assess cost-effectiveness based on information collected at Months 3 and 6 (short-term), Month 12 (mid-term), and month 18 (long-term), respectively. The long-term analysis will extrapolate the intervention effect to lifetime and use YOLS and QALY as the effectiveness measure. A 3% discount rate will be applied to costs and outcomes accrued in the second year and forward. First, we will work with the lead biostatistician of

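### No adjustment for baseline EQ-5D is specified in the QALY comparison, so a chance baseline difference can rival the QALY gain expected from extra quitters

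*Combined protocol and SAP*

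**What the plan says.** Table 1 has a row beginning "EQ-5D (for health utilities", marked at baseline and at months 3, 6, 12 and 18. Under Baseline Assessment and Randomization, women are assigned only after the baseline questionnaires, so the baseline utility is a proper pre-randomization covariate. Cost Effectiveness, Measures of Effectiveness, adds QALYs as a further effectiveness measure and says the team will "calculate QALY from the health utilities obtained from the EQ-5D".

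Methods overview defines the ICER as "the difference in mean costs between the new and standard treatment divided by the difference in mean effectiveness" for the two treatments. Under Analysis, once missing values have been handled, the order is stated: "Next, we will perform deterministic CEA based on ICER". A Bayesian acceptability curve follows, with distributions given for costs and for abstinence but none for utility or QALY. Last comes a regression of each woman's net benefit on treatment arm and covariates, which are not listed. QALYs are assigned to the long-term analysis, where the effect is extrapolated to lifetime.

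EQ-5D appears neither among the minimization factors nor among the covariates of the primary abstinence model. For the mediation analysis, by contrast, Data Analysis Approach does commit to adjusting for the mediators' baseline values.

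**The concern.** A QALY built as the area under the utility curve contains the baseline utility, and baseline utility also predicts every later value. If one arm happens to start with better utility, an unadjusted difference in mean QALYs credits that head start to treatment. The benefit that can arrive through quitting is diluted, because the design effect makes only about 12 more women in every 100 abstinent. A modest imbalance could therefore set the size, or even the sign, of the trial-period QALY difference. Leaving the regression covariates unnamed also allows the adjustment to be chosen after the data are seen.

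**Working it through.** **The plan's own figures.** The documents give no figure for EQ-5D or QALYs, so the design figures are checked first. The Power section says "a sample size of 300 (150 per group) will provide 80% power" for "abstinence rates of 10% and 21.9% in ST and MAPS respectively". At two-sided 0.05, with mean proportion 0.1595:

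n = [1.96·√(2·0.1595·0.8405) + 0.842·√(0.10·0.90 + 0.219·0.781)]² / 0.119² = 148 per arm.

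Power at 150 per arm is 0.807, so the figure reproduces. The 0.376 SD figure for continuous mechanisms also reproduces: 112 per arm gives power 0.800.

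**Inputs.** From the documents: 150 per arm, an abstinence difference of 21.9 − 10 = 11.9 points, the EQ-5D visit schedule, and 3% discounting from the second year. Assumed, because the documents do not give them: utility SD 0.10-0.25, equal correlation r of 0.3-0.9 between any two visits, and a utility gain u of 0.02-0.10 per extra quitter. Complete data and no help from minimization are also assumed.

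**QALY weights.** The trapezoidal rule over 0, 0.25, 0.5, 1 and 1.5 years, with months 12-18 divided by 1.03, gives weights 0.125, 0.250, 0.375, 0.493 and 0.243. The total is 1.485 years, of which 1.360 falls on follow-up visits.

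**Chance baseline difference.** SE = SD·√(2/150). At SD 0.20 this is 0.023; over SD 0.10-0.25 it is 0.012-0.029.

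**Carry-over into QALYs.** Each unit of baseline difference carries 0.125 + r·1.360: 0.533, 0.805, 1.077 and 1.349 at r = 0.3, 0.5, 0.7 and 0.9. One-SE carry-over in QALYs:

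| SD | r 0.3 | r 0.5 | r 0.7 | r 0.9 |
|---|---|---|---|---|
| 0.10 | 0.0062 | 0.0093 | 0.0124 | 0.0156 |
| 0.15 | 0.0092 | 0.0139 | 0.0187 | 0.0234 |
| 0.20 | 0.0123 | 0.0186 | 0.0249 | 0.0312 |
| 0.25 | 0.0154 | 0.0232 | 0.0311 | 0.0390 |

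**Gain through extra quitters.** 0.119·u·1.360 = 0.0032, 0.0081 and 0.0162 QALY for u = 0.02, 0.05 and 0.10. The one-SE carry-over is at least as large in 16, 15 and 8 of the 16 cells respectively.

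**Chance that an imbalance against MAPS exceeds the gain.** This is 1 − Φ(gain / one-SE carry-over). At SD 0.20 and r = 0.5 it is 43%, 33% and 19% for the three gains. Over the whole grid it runs from 0.4% (SD 0.10, r 0.3, u 0.10) to 47% (SD 0.25, r 0.9, u 0.02).

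**Effect of adjustment.** The share of QALY variance removed is (0.125 + 1.360r)² / [(1 − r)·Σw² + r·(Σw)²], with Σw² = 0.520 and (Σw)² = 2.207. This is 28%, 48%, 68% and 89% at r = 0.3, 0.5, 0.7 and 0.9, whatever the SD. At SD 0.20 the SE of the QALY difference falls from 0.027 to 0.020 (r 0.5) and from 0.030 to 0.017 (r 0.7). With 112 per arm all SEs rise by √(150/112), about 16%. The familiar r² rule (25% and 49% at r 0.5 and 0.7) applies to a single follow-up value and understates the reduction for an area that includes baseline.

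**The case against.** A reader might infer that the plan compares QALYs only as raw arm means. The documents do not support that. The ICER sentence is a general definition in an overview, and the plan commits to a covariate-adjusted net-benefit regression in which baseline EQ-5D is neither included nor excluded. Nor does the plan state a QALY distribution for the acceptability curve, so it cannot be said to use raw means. What remains is that the ICER and the curve, the two results the plan undertakes to report, have no stated adjustment. The regression itself is motivated by moderators rather than by baseline imbalance.

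A reader might also infer that imbalance outweighs any plausible QALY gain. It does not. At SD 0.10 and r = 0.3, a gain of 0.016 exceeds even a 1.96-SE imbalance (0.012). MAPS also targets stress and negative affect, so it could raise utility by routes other than quitting. A direct shift of 0.376 SD, borrowed from the mechanism calculation, would give 0.376·0.20·1.360 = 0.102 QALY at SD 0.20, against a 1.96-SE imbalance of 0.024-0.061 over r 0.3-0.9.

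Third, QALYs belong to the lifetime analysis, and how EQ-5D enters it is not stated. If utilities merely weight life-years modelled from abstinence, a baseline difference between arms need not carry through in the way calculated here. This objection stands, and it limits the figures to the trial-period component. Minimizing on age, stage, treatment status and time since diagnosis may also reduce the imbalance somewhat.

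**Conclusion.** The concern holds as a gap in specification with a real cost in precision. Baseline utility is measured before randomization, yet no economic analysis is committed to using it. At assumed SD 0.20 and r 0.5-0.7, an ordinary one-SE imbalance is worth 0.019-0.025 QALY over 18 months, against 0.003-0.016 from extra quitters. Whether imbalance dominates depends on the SD, the correlation and the utility gain per quitter, none of which the documents give. The variance reduction does not depend on the SD or the utility gain, only on the correlation structure.

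It would be wrong to read this as bias: over repeated randomization the unadjusted difference is unbiased. The error is conditional on the imbalance observed. It concerns a secondary measure under Aim 3 and leaves the primary abstinence test untouched. It should be corrected, because the better estimate uses data already in hand.

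**What to change.** State in the Cost Effectiveness section that:

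- the trial-period QALY difference will be estimated by regression of individual QALYs on arm and baseline EQ-5D utility;
- this adjusted difference will be used wherever QALY is the effectiveness measure in the ICER and the acceptability curve;
- baseline EQ-5D utility is a named covariate in the QALY net-benefit regression.

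The same paragraph should say how trial utilities feed the lifetime QALY, since the adjustment matters only as far as they do. The change needs a few sentences in the plan and no new data, visits or participants.
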